1.3 DETERMINATION OF SAMPLE SIZE

The sample size of the study is determined based on power calculations for the primary endpoint of annualized rate of acute moderate or severe COPD exacerbations over the 52-week treatment period. Assuming the number of exacerbations follows a negative binomial distribution with a dispersion parameter of 1, a placebo annualized rate of exacerbations of 1.5, an average treatment duration of 0.95 year (to account for an average of 5% of the planned treatment period with missing data), and a randomization ratio of 1:1 to the two treatment arms, with 924 randomized patients (462 for each treatment arm), the study will have 90% power to detect a 25% relative risk reduction (ie, annualized rate of 1.125 for the dupilumab group) in the annualized rate of moderate or severe COPD exacerbations at the 2-tailed significance level of $\alpha=0.049$ (an administrative penalty of 0.001 will be taken from the significance level used at final analysis due to a planned interim analysis; details are provided in [Section 3](#)).

Patients will be randomized using a 1:1 randomization ratio to dupilumab 300 mg q2w or placebo. Randomization will be stratified by country and by ICS dose (high dose ICS [yes/no]) at baseline.

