following sensitivity analyses will be conducted to assess the robustness of the conclusion based on the primary analysis.

Pattern mixture model - multiple imputation (PMM-MI)

For each patient with missing data of moderate or severe exacerbation events, individual bi-weekly event probability will be estimated using observed data with adjustment of the planned treatment group, region (pooled country), ICS dose at baseline (high dose ICS [yes/no]), smoking status at screening (current smokers or not), baseline disease severity (as % predicted post-bronchodilator FEV1), and number of moderate or severe COPD exacerbation events within one year prior to the study (≤ 2 , 3, or ≥ 4). The total number of AECOPD moderate or severe events (on bi-weekly basis) will be calculated based on data imputed using multiple imputation.

Control-based PMM-MI

For each patient with missing data of moderate or severe exacerbation events, individual bi-weekly event probability will be estimated using observation in the placebo arms only, with adjustment of region (pooled country), ICS dose at baseline (high dose ICS [yes/no]), smoking status at screening (current smokers or not), baseline disease severity (as % predicted post-bronchodilator FEV1), and number of moderate or severe COPD exacerbation events within one year prior to the study (≤ 2 , 3, or ≥ 4). The total number of AECOPD moderate or severe events (on bi-weekly basis) will be calculated based on data imputed using multiple imputation.

Tipping point analysis

For each patient with missing data of moderate or severe exacerbation events, the bi-weekly event will be imputed in a similar fashion as PMM-MI based on various odds values. If the patient is on dupilumab, the predicted odds will be increased; if the patient is on Placebo, the predicted odds value will be decreased. The adjusted rate will then be used to impute the number of events that would occur during the missing observation period. A sequence of increasing/decreasing ratio will be used to generate different imputed datasets.

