Appendix J Handling of missing data

Annualized rate of moderate or severe exacerbation events during the 52-Week period

- *Pattern mixture model - multiple imputation (PMM-MI)*

Step 1. The 52-week observation period is partitioned into bi-weekly (2-week) segments.

By clinical definition, a patient can have at maximum 1 moderate or severe exacerbation event per two weeks. For each patient, his/her event count over 52 weeks is broken down into a series of binary outcomes across each of the 26 bi-weekly segments (52 weeks). In the analysis, for each patient, in each bi-weekly segment, an imputation flag (impute_{fl}) will indicate whether the patient needs imputation in that segment.

Step 2. Estimation for the bi-weekly binary event probability using observed data

Within each bi-weekly segment, the logistic regression model will be fitted to the observed data to model coefficient estimates and the estimated variance-covariance matrix, with adjusting for the planned treatment group, region (pooled country), ICS dose at baseline (high dose ICS [yes/no]), smoking status at screening (current smokers or not), baseline disease severity (as % predicted post-bronchodilator FEV₁), and number of moderate or severe COPD exacerbation events within one year prior to the study (≤ 2 , 3, or ≥ 4). From the posterior distribution of the model coefficients, we randomly draw 40 sets of iid samples. As a result, for each patient and in each bi-weekly segment, 40 estimated probabilities can be obtained by using the 40 samples of coefficients and the patient's covariate values.

Step 3. Multiple Imputation of binary event by bi-weekly segment after study withdrawal

If a patient withdraws from the study at the k th ($1 \leq k < 14$) day of Segment i prior to Week 52, and experienced a moderate or severe exacerbation within the first k days, this patient will be considered as "observed" (impute_{fl}=0) up to Segment i and will need imputations (impute_{fl}=1) from Segment $i+1$ to Segment 26 (Week 52).

If a patient withdraws from the study at the k th ($1 \leq k < 14$) day of Segment i prior to Week 52, and has no moderate nor severe exacerbation in Segment i , this patient will be considered as "observed" (impute_{fl}=0) up to Segment $i-1$ and will need imputations (impute_{fl}=1) from Segment i to Segment 26 (Week 52).

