For a patient who needs imputation from Segment $i+1$ to Segment 26, in each bi-weekly segment, 40 independent random samples will be respectively drawn from 40 estimated Bernoulli distributions, whose probabilities are obtained in Step 2.

For each patient who early withdraws from the study, 40 sets of complete event count data can be obtained by summing the observed event count prior to withdrawal and each series of imputed binary events after withdrawal up to Week 52.

Step 2 and 3 can be realized by using PROC MI in SAS. Sample code can be found below:

```
proc mi data =dd seed =9816388 nimpute =40 out =outdata;
by month;
class outcome trt01pn cnt ygr1 ics copdnum;
monotone re g (fev1bl/details) ;
logistic (outcome=trt01pn cntygr1 ics smokin g fev1bl copdnum /details
DESCENDING);
var cntygr1 ics smoking fev1bl trt01pn copdnum outcome;
run ;
```

Step 4. Combining MI results by Rubin's formula

A negative binomial model with the same set of covariates as in the primary analysis will be fitted with 40 sets of complete datasets obtained in Step 3, so as to obtain 40 sets of treatment effect estimates (in log-scale) and p-values accordingly. Log transformed observation duration will be the offset variable for patients who complete the 52-Week treatment/study period, and log transformed 52 weeks will be the offset variable for patients who discontinue the study before Visit 16 (Week 52). At last, the SAS MIANALYZE procedure will be used to generate statistical inferences by combining results (in log-scale) from the 40 analyses using Rubin's formula. These and their confidence interval limits are then exponentiated to derive relative rates. Of note, the rule will be applied on the log risks and log risk ratio.

Step 4 can be realized by using PROC MIANALYZE in SAS. Sample code can be found below

```
proc mianalyze data=r_r_conv;
by Label;
modeleffects Estimate;
stderr StdErr;
ods output ParameterEstimates=r_r_pooled;
run ;
proc mianalyze data=aer_conv;
by TRT01PN;
modeleffects Estimate;
stderr StdErr;
ods output ParameterEstimates=aer_pooled;

run ;
/* estimated RR and corresponding 95% CI */
data pouttx;
set r_r_pooled;
if Parameter="txval";

rr = exp(estimate);
```

run ;

- ***Control-based PMM-MI***

All steps are the same as the aforementioned approach except in **Step 2**: the individual bi-weekly mean probability will be calculated based on observations in matching placebo arms only, with adjustment of missing observation duration.

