- ***Tipping point analysis***

The tipping point analysis for severe exacerbation events will use the similar approach as PMM-MI with tipping values for the odds.

Step 1. Estimation for the bi-weekly binary event probability using observed data

Within each bi-weekly segment up to Week 52, the logistic regression model will be fitted to the observed data to obtain the model coefficient estimates and the estimated variance covariance matrix, with adjusting for the planned treatment group, region (pooled country), ICS dose at baseline (high dose ICS [yes/no]), smoking status at screening (current smokers or not), baseline disease severity (as % predicted post-bronchodilator FEV1), and number of moderate or severe COPD exacerbation events within one year prior to the study (≤ 2 , 3, or ≥ 4). From the posterior distribution for the model coefficients, we randomly draw 40 sets of iid samples. As a result, for each patient and in each segment, 40 estimated binary event probabilities can be obtained by using the 40 samples of coefficients and the patient's covariate values.

Step 2. Tip on the bi-weekly binary odds (the probability of having an event in the segment over the probability of being event-free in the segment)

Within each segment, for the patients from the placebo group and need imputation in that segment, the estimated odds for binary event will be deflated by decreasing a positive amount; for the patients from the treatment group and need imputation in that segment, the estimated odds for binary event will be inflated by increasing a positive amount. After the deflation/inflation, 40 sets of binary event probabilities can be obtained for the placebo and treatment groups, respectively.

Step 3. Multiple Imputation of binary event by bi-weekly segment after study withdrawal

For a patient who needs imputation from Segment $i+1$ to Segment 26, in each segment, 40 independent random samples will be respectively drawn from 40 estimated Bernoulli distributions, whose probabilities are obtained in Step 2.

For each patient who early withdraws from the study, 40 sets of complete event count data can be obtained by summing the observed event count prior to withdrawal and each series of imputed binary events after withdrawal up to Week 52.

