Step 4. A negative binomial model with the same set of covariates as in the primary analysis will be fitted to the 40 sets of complete datasets obtained in Step 3, so as to obtain 40 sets of treatment effect estimates and p-values accordingly. Log transformed observation duration will be the offset variable for patients who complete the 52-Week treatment/study period, and log transformed 52 weeks will be the offset variable for patients who discontinue the study before Visit 16 (Week 52). Then, the SAS MIANALYZE procedure will be used to generate statistical inferences by combining results from the 40 analyses using Rubin's formula.

Step 2, 3 and 4 will be repeated iteratively until the p-value for combined treatment effect of dupilumab compared to placebo estimated in Step 4 is > 0.05 or the maximum applicable treatment effect has been reached.

Change from baseline in pre-BD FEV1 at Week 12

- ***Pattern mixture model-multiple imputation (PMM-MI)***

Step 1. Monotone missing pattern was induced by Markov Chain Monte Carlo (MCMC) method using PROC MI: for patients who have missing values at intermediate visits, but have value at subsequent visits, the intermediate missing values were imputed assuming a multivariate normal distribution over observations from all visits. 40 datasets with a monotone missing pattern will be obtained using this method.

Step 2. For each of the imputed dataset with monotone missing pattern obtained in Step 1, the remaining missing data will be imputed using the regression method for the monotone pattern with adjustment for covariates including treatment groups, age, sex, height, region (pooled country), ICS dose at baseline (high dose ICS [yes/no]), smoking status at screening (current smokers or not), and baseline pre-BD FEV1. All available data in the monotone missing pattern data will be used. 40 fully imputed datasets are obtained.

Step 3. Each of the 40 complete datasets will be analyzed using an ANCOVA model with change from baseline in pre-BD FEV1 at Week 12 as the response variable, treatment, age, sex, height, region (pooled country), ICS dose at baseline (high dose ICS [yes/no]), smoking status at screening (current smokers or not), and baseline pre-BD FEV1 value as covariates. Then the SAS MIANALYZE procedure will be used to generate statistical inferences by combining results from the 40 analyses using Rubin' s formula.

- ***Tipping point analysis***

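### Appendix J imputes missing exacerbations without the patient's own on-study events: the PMM-MI standard error is about 3% too small at the planned missing time, and its rate ratio can drift if withdrawal follows events in one arm

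*SAP*

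**What the plan says.** - **Sample size (SAP Section 1.3).** "Assuming the number of exacerbations follows a negative binomial distribution with a dispersion parameter of 1", with a placebo rate of 1.5 per year, 1.125 on dupilumab, 462 patients per arm and a mean of 0.95 year observed (5% missing).
- **Primary analysis (SAP Section 2.4.4.1).** A negative binomial model with log observation time as offset. Events after study withdrawal are not imputed.
- **PMM-MI (SAP Section 2.4.4.1).** For patients with missing data, the "individual bi-weekly event probability will be estimated using observed data with adjustment of the planned treatment group", plus region, ICS dose, smoking, % predicted FEV1 and the prior-year exacerbation category.
- **Appendix J, Steps 1-3.** The year is cut into 26 two-week segments with at most one event each. "Within each bi-weekly segment, the logistic regression model will be fitted to the observed data". For each missing segment, "40 independent random samples will be respectively drawn from 40 estimated Bernoulli distributions". The sample code lists "var cntygr1 ics smoking fev1bl trt01pn copdnum outcome"; the only history variable there is the pre-study category. Observed events are added to the imputed ones to form the total, but they do not inform the imputation.
- **Appendix J, Step 4.** A negative binomial model is fitted to each completed dataset, with a 52-week offset for withdrawals, and results are combined by Rubin's formula.
- **Reuse.** The control-based version keeps every step except that "the individual bi-weekly mean probability will be calculated based on observations in matching placebo arms only". The tipping point starts in the same way ("Within each bi-weekly segment up to Week 52, the logistic regression model will be fitted to the observed data") and shifts the odds "until the p-value for combined treatment effect of dupilumab compared to placebo estimated in Step 4 is > 0.05".

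For FEV1, by contrast, the same appendix imputes by monotone regression using all available data.

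**The concern.** A negative binomial model with dispersion 1 says that patients differ in underlying rate beyond their covariates. A patient's observed count is then informative about the events not seen. Appendix J discards that information and draws segments independently, yet analyses the completed data with a model that assumes the information exists.

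Two consequences follow. First, imputed patients are pulled towards the arm average, so the fitted dispersion and the standard error fall without any added information. Second, if withdrawal is related to events already observed, the primary likelihood can largely absorb this because it uses those events. An imputation model that omits them cannot. At stake is how far the robustness checks can be trusted, not the primary result.

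**Working it through.** **1. The plan's own figure.** With t = 0.95, k = 1 and n = 462:

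Var(log RR) = [1/(1.5 × 0.95) + 1 + 1/(1.125 × 0.95) + 1]/462 = 3.637/462, so SE = 0.0887.

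z = 0.2877/0.0887 = 3.24. Against the critical value 1.969 for two-sided 0.049, power is 0.8986. The stated 90% is reproduced (464.3 per arm would give exactly 90%).

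**2. What the omission does to one patient.** For a placebo patient leaving at Week 26 with y events, at k = 1, expected further events = 1.5 × 0.5 × (1 + y)/(1 + 0.75).

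- y = 0: 0.75 × 1/1.75 = 0.43
- y = 3: 0.75 × 4/1.75 = 1.71

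Appendix J draws about 0.75 for both if their covariates are equal.

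**3. Standard error under random withdrawal.** The simulations used 462 per arm, 26 binary segments, gamma frailty, 40 imputations and no baseline covariates.

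- *Set A* (frailty tuned to a fitted k of about 1.02; 300-400 trials per scenario), 10% withdrawing, about 5% missing time: primary SE 0.0901, PMM-MI 0.0872; 0.0872/0.0901 = 0.968. Other 5% scenarios at k about 1 gave 0.962 to 0.971. Fitted dispersion fell from about 1.03 to 0.93. The empirical SD of both estimators was 0.096, so the smaller SE is not real precision.
- *Set B* (2,000 trials; fitted complete-data dispersion 0.87): primary 0.0871, PMM-MI 0.0845, no withdrawal 0.0855; 0.0845/0.0871 = 0.970. PMM-MI coverage was 93.9%, primary 94.3%.
- *10% missing time (assumed)*: about 6% lower in Set A. In Set B, 0.0838/0.0887 = 0.945.
- *Smaller dispersion*: about 2% lower at k of about 0.45 (Set A) and at k = 0.6 (Set B).
- *With a prior-year covariate* (assumed shares 55/25/20% and rate multipliers 0.80/1.05/1.50, variance 0.072; residual k = 0.865, since 1.072 × 1.865 = 2): ratio 0.972 with 10% withdrawing and 0.947 with 20%.

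**4. Rate ratio when withdrawal depends on events in one arm only** (Set A; random in the other arm; about 5% missing in each). PMM-MI relative to primary:

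| Withdrawal hazard after an event | Dependence in dupilumab arm | Dependence in placebo arm |
|---|---|---|
| × 1.5 | -0.3% | — |
| × 2 | -0.6% | +0.8% |
| × 3 | -1.2% | +1.3% |
| × 5 | -1.9% | — |
| every withdrawal directly after an event | -5.0% | +5.0% |

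A hazard rising × 1.5 or × 2 with each event, in the dupilumab arm, gave -1.4% and -3.1%. When both arms shared the event-only rule, the drift was about +0.2%.

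In Set B, hazards proportional to 1 + events and to 0.25 + events gave log rate ratio shifts of -0.010 and -0.021 for dupilumab-arm dependence, and +0.013 and +0.023 for placebo. The shifts were +0.004 and +0.005 when both arms shared the dependence. With dupilumab-arm dependence, the primary rate ratio stayed within 0.002 of its no-withdrawal value.

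**5. The other two analyses** (Set B).

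- *Random withdrawal*: the control-based SE was 0.0842 against an empirical SD of 0.0820. The median odds multiplier at the tipping point was 2.99, against 3.21 with count-conditional imputation. Neither is too favourable.
- *Dupilumab-arm dependence*: the tipping multiplier was 11% (1 + events) to 31% (0.25 + events) larger than with count-conditional imputation.
- *Control-based minus primary log rate ratio, dupilumab-arm dependence*: +0.005 and -0.006 for the two hazards, against +0.016 and +0.017 with count-conditional imputation.

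**6. After conditioning on the patient's own count** (Set A). The SE ratio to primary was 0.999 under random withdrawal, 1.001 at × 3, 1.002 at × 5 and 1.009 when every withdrawal follows an event. The rate ratio relative to primary was 1.000 in all four. With the covariate of step 3, the SE ratios were 0.997 and 0.994.

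**The case against.** The strongest reply is that little depends on this.

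- **The formal conclusion is safe.** The primary analysis does not impute, and SAP Section 2.4.4.3 calls the study positive on the primary endpoint alone. This stands.
- **Missing data should be limited and visible.** Patients who stop treatment stay in follow-up and their events count, so only study withdrawal creates missing data. SAP Section 2.4.4.1 also tabulates the number, reasons and timing of withdrawals by arm. This stands, but a table does not correct the imputation.
- **Random withdrawal does little damage.** In Set B at rate ratio 1, PMM-MI rejected in 5.4% of trials against 4.8% for the primary (nominal 4.9%, Monte Carlo error 0.5 points). At the planned effect, PMM-MI was significant and the primary not in 24 of 2,000 trials, with the reverse in 4. A reader might infer from a 3% shortfall that type I error is inflated: 2[1 - Φ(1.969 × 0.967)] = 0.057. The simulation does not demonstrate that.
- **One-arm dependence is assumed.** A reader might also infer that the robustness checks favour dupilumab. The documents give 5% missing time but no withdrawal proportion, timing or mechanism. The direction reverses for placebo, and the drift nearly vanishes if both arms behave alike.
- **The tipping figures are fragile.** They use one path (odds multiplied in one arm and divided in the other), assumed hazards and no covariates. Neither SAP Section 2.4.4.1 nor Appendix J sets a threshold for a plausible shift, so a larger multiplier changes no planned decision.
- **Absolute standard errors in Set B are not the plan's.** At 0.0871, the primary SE lies below the 0.0887 implied by SAP Section 1.3. The ratio is the result to keep.

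These points limit size and confidence. They do not make an imputation that ignores observed outcomes consistent with the model that then analyses it.

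**Conclusion.** The concern holds as a minor, correctable fault in the sensitivity analyses, of the could-fix kind. The standard-error shortfall is well supported at 5% missing time and dispersion of about 1, and it shrinks as the covariates absorb dispersion. The rate-ratio drift is conditional on event-related withdrawal in one arm. Its size depends on how steeply the hazard rises, so it should be quoted with that hazard and its direction. The 11-31% tipping-point inflation carries lower confidence. The documents do not support extending the fault to the primary estimate or the formal conclusion. Nor, under random withdrawal, are the control-based and tipping-point results shown to be too favourable.

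**What to change.** In Appendix J, Steps 2-3, condition each imputation on the patient's on-study event count and observed time, by negative binomial conditional imputation:

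1. Draw the rate parameters and dispersion k from the fitted primary model.
2. Draw the patient's frailty from a gamma distribution with shape 1/k + observed count and rate 1/k + expected count over the observed time. With no observed time this is Gamma(1/k, 1/k), so withdrawal in the first segment is covered.
3. Draw the missing count from frailty × rate × missing time.

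Use the same engine for the control-based analysis (placebo rate after withdrawal, frailty from the patient's own count) and for the tipping point. Align the wording in SAP Section 2.4.4.1.

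The cost is SAP text and some reprogramming; no new data are needed. PMM-MI intervals become about 3% wider at the planned missing time. PMM-MI, as a missing-at-random check, will nearly reproduce the primary, so the robustness information will come from the control-based and tipping-point analyses.
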